## **MLN0128**

### **Clinical Study Protocol C31001 Amendment 6, EudraCT: 2014-001921-34**

MLN0128. The sponsor's project clinician should be contacted before any dose modification in MLN0128 for any patient in the study.

#### **6.4 Excluded Concomitant Medications and Procedures**

All prescription and over-the-counter medications, including influenza vaccines, taken by a patient as of the first MLN0128 administration through 30 days following the last dose will be recorded on the designated case report form.

The following medications/therapies are prohibited during the study:

- Other investigational agents, including mTOR, PI3K, and AKT inhibitors.
- Other anticancer therapies, including chemotherapy, immunotherapy, radioimmunotherapy, targeted agents, radiation, or surgery (patients can have palliative radiation or surgery during the study for pre-existing lesions).
- Systemic corticosteroids (either IV or oral steroids, excluding inhalers), unless necessary for treatment of an MLN0128-related AE (eg, rash).
- Strong CYP1A2 inhibitors and CYP inducers should be administered with caution and at the discretion of the investigator (see Section 14.4 for a list of these agents).
- Antiepileptic drugs for patients with a history of treated brain metastasis.
- Concomitant administration of any proton pump inhibitor (PPI) is not permitted during the study. Patients receiving PPI therapy before enrollment must stop using the PPI for 7 days before their first dose of study drugs. Examples of PPIs include omeprazole, esomeprazole, pantoprazole, lansoprazole, and rabeprazole.
- Histamine H2 receptor antagonists may be allowed, if needed provided that the histamine H2 receptor antagonist is not taken within 12 hours before and within 6 hours after study drug administration. Patients receiving histamine H2 receptor antagonists before enrollment must stop using these medications for at least 24 hours before their first dose of study drug. Examples of histamine H2 receptor antagonists include ranitidine, famotidine, and nizatidine. Cimetidine, a moderate CYP1A2 inhibitor, is not recommended as a first choice H2 receptor antagonist (see Section 14.4).

## **MLN0128**

### **Clinical Study Protocol C31001 Amendment 6, EudraCT: 2014-001921-34**

- Administration of neutralizing antacids and calcium preparations is permitted except from 4 hours before until 2 hours after MLN0128 administration. Some antigas preparations may also have antacid properties, and should also not be permitted from 4 hours before until 2 hours after study drug administration.

#### **6.5 Permitted Concomitant Medications and Procedures**

Prophylactic use of antiemetic (including ondansetron and granisetron), antinausea, and antidiarrheal medications is encouraged, and these may be administered before the first dose of MLN0128, as needed throughout the study before each dosing, and as clinically indicated per standard practice.

Concomitant treatment with bisphosphonates is permitted for treatment of osteoporosis or management of existing bone metastases if initiated at least 4 weeks before administration of the first dose of MLN0128. Bisphosphonates should be given after Cycle 1 to minimize confounding factors that may contribute to potential drug-related toxicities.

Other medications considered necessary for the safety and wellbeing of the patient may be administered at the discretion of the investigator. Any concomitant medications added or discontinued during the study should be recorded on the electronic case report form (eCRF).

#### **6.6 Precautions and Restrictions**

No dietary restrictions will be imposed on study patients other than daily fasting for glucose monitoring (refer to Section [7.4.16](#)).

Patients who show evidence of hyperglycemia during the study should be encouraged to follow a low-carbohydrate diet.

#### **6.7 Management of Clinical Events**

##### **6.7.1 Management of Hyperglycemia**

In addition to obtaining fasting serum glucose levels at the clinic visits as outlined in the [Schedule of Events](#), all patients will be provided with a glucometer and trained in its use to monitor their daily predose fasting blood glucose (FBG) levels at home. Patients will be instructed to notify the study staff immediately of any abnormal readings (ie,  $\geq 150$  mg/dL) for further instructions on the management of their hyperglycemia. Hyperglycemia observed during home glucose monitoring should be confirmed in the clinic. Investigators will be responsible for reviewing the home glucose monitoring logs for hyperglycemia. If no

irregularities in the FBG level are observed during a minimum of 6 consecutive months, then the frequency of in-home fasting glucose testing may be reduced to twice weekly if the investigator approves. Patients will continue to notify the investigator of FBG levels  $\geq 150$  mg/dL, and if blood glucose levels are not well controlled, or if they require either oral hypoglycemic agents or insulin to control blood glucose levels, then the frequency of in-home testing of FBG levels will be reinstated to daily. Guidelines for management of hyperglycemia are presented in [Table 6-1](#).

**Table 6-1 Management of Hyperglycemia**

Grade	Description	Treatment	MLN0128 Dose Modification
1	FBG>ULN–160 mg/dL	Continue close monitoring of blood glucose. Initiate oral hypoglycemic agent.	None
2	FBG>160–250 mg/dL	Initiate oral hypoglycemic agent and/or insulin if not well controlled on oral agent.	None
$\geq 3$	FBG>250 mg/dL	Initiate oral hypoglycemic agent and/or insulin.	Hold drug until $\leq$ Grade 2. Resume MLN0128 based on timing of recovery: 
 
• <math>\leq 1</math> week: resume at same dose and schedule.
 
• <math>>1</math> but <math>\leq 2</math> weeks: reduce dose. (a)
 
• 2 weeks: stop MLN0128 and discontinue patient from the study.
 

**Prevention/Prophylaxis**

- Follow fasting serum glucose levels during clinic visits.
- Monitor home glucometer test results.
- Check HbA1c levels every 3 months during therapy.
- Recommend lifestyle modifications, as appropriate (balanced diet, limited alcohol consumption, increased physical activity).
- Most episodes of Grade 1 and 2 hyperglycemia respond quickly to oral metformin. Early initiation of therapy is recommended to prevent higher-grade hyperglycemia.
- FBG levels  $\geq 150$  mg/dL by glucometer should be followed by closer monitoring of serum glucose and possible intervention.

QD $\times$ 5D=once daily for 5 days each week.

(a) Phase 1b Part 1 cohorts: for patients receiving a starting dose of 5 mg, reduce by 20% (to 4 mg). If dose modification is required for patients receiving  $\leq 4$  mg QD, then the frequency of dosing should be decreased to QD $\times$ 5D, rather than decreasing the daily dose administered. For all other patients: the initial dose reduction should be from 4 mg to 3 mg, with further reduction to 2 mg if necessary.

If any fasting serum glucose reading performed at the site indicates hyperglycemia ( $>$ ULN or  $\geq 110$  mg/dL), the study staff should first confirm that the patient was fasting at the time

**MLN0128****Clinical Study Protocol C31001 Amendment 6, EudraCT: 2014-001921-34**

of the blood draw (ie, nothing by mouth for at least 8 hours before). To aggressively manage the hyperglycemia per standard clinical practice, the following guidelines are provided to aid the investigator in initiating antiglycemic therapies.

Based on the clinical experience in MLN0128 trials, most episodes of hyperglycemia observed have been Grade 1 or Grade 2 and have responded quickly to oral metformin. Hyperglycemia has not been dose-limiting since instituting a standard regimen for early treatment of hyperglycemia. All patients developing hyperglycemia on the study should have their glucose closely monitored by study staff. The investigator may choose either to continue close monitoring of patients who develop Grade 1 hyperglycemia (fasting serum glucose  $>ULN \leq 160$  mg/dL) or consider initiating treatment with an oral hypoglycemic agent, such as metformin. All patients with  $\geq$ Grade 2 hyperglycemia (fasting serum glucose  $>160$  mg/dL) must be treated aggressively with oral hypoglycemic agents and/or insulin as clinically indicated while continuing on MLN0128 treatment. The investigator should consult an endocrinologist if needed to aid in optimizing the hyperglycemia treatment plan of the patient.

It is recommended that patients be treated initially with a fast-acting insulin sensitizer, such as metformin at 500 mg orally QD, and titrate up to a maximum of 1000 mg orally twice daily as needed. Concurrent addition to metformin of dipeptidyl peptidase-4 inhibitors (eg, sitagliptin or vildagliptin) and/or insulin should also be considered. Oral sulfonylureas (eg, glipizide or glyburide) should be used with caution due to the higher risk of inducing hypoglycemia in patients. The dose of oral hypoglycemic agents should be adjusted in patients with renal insufficiency.

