### **6.3 Dose-Modification Guidelines for the Phase 2 Portion of the Study**

#### **6.3.1 Dose Modification or Treatment Delay for MLN0128-Related Toxicity**

Based on the outcome of a safety and tolerability analysis performed in the phase 1b portion of the study, MLN0128 4 mg QD in combination with either exemestane or fulvestrant was determined as the phase 2 starting dose. Another safety and tolerability assessment will be performed during the phase 2 portion of the study where the first 6 patients treated with MLN0128 4 mg QD in combination with exemestane or fulvestrant who have completed 2 cycles of treatment with MLN0128 will be evaluated for TEAEs. Enrollment of patients into the study will continue during this safety and tolerability assessment.

In addition, during the phase 2 portion of the study, both tolerability and need for dose reductions and/or modifications will continue to be monitored for all patients in all cycles. If, based on this assessment, the 4 mg QD starting dose identified in Part 2 of the phase 1 portion is deemed unfavorable, in conjunction with agreement of the study investigators and the medical monitor, the starting dose may be adjusted to 2 or 3 mg QD for all newly enrolled patients to improve long-term tolerability. Patients who were enrolled at 3 or 4 mg QD in Part 2 of the phase 1 portion and the phase 2 portion will be maintained at this dose unless dose modifications are required due to individual tolerability. A starting dose reduction, if required, will be documented to all study sites by formal written communication.

MLN0128 administration should be withheld for MLN0128-related toxicities that are  $\geq$ Grade 3 despite supportive treatment per standard clinical practice. If the event resolves to Grade 1 or baseline values within 2 weeks of interrupting treatment, the patient may resume study treatment at a 25% to 50% dose reduction (ie, 2 mg QD). Alternatively, if dose modification is required for patients receiving 2 mg QD, then the dosing frequency should be decreased to 5 days per week instead of decreasing the daily dose administered. If MLN0128 dosing is delayed for more than 14 consecutive days for MLN0128-related toxicity despite supportive treatment per standard clinical practice, or more than 2 dose reductions of MLN0128 are required in a patient, stop MLN0128 therapy, discontinue the patient from the study, and complete the EOT visit within 30 to 40 days after the last dose of

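### Section 6.7.1 both continues and holds MLN0128 when fasting glucose exceeds 250 mg/dL

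*Protocol*

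**What the plan says.** Protocol Section 6.7.1 handles hyperglycemia in two places.

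- **The table.** The opening paragraph sends the reader to Table 6-1: "Guidelines for management of hyperglycemia are presented in" that table. The table has a column for changes to the MLN0128 dose. Grade 2 (above 160 to 250 mg/dL) calls for no change. At Grade 3 or higher (above 250 mg/dL) the entry begins "Hold drug until", with recovery to Grade 2 or lower as the release condition, and then "Resume MLN0128 based on timing of recovery": same dose after recovery within one week, reduced dose after more than one and up to two weeks, and otherwise stop.
- **The text after the table.** This is introduced with the words "the following guidelines are provided to aid the investigator in initiating antiglycemic therapies". It then says that all patients at Grade 2 or higher, defined as fasting serum glucose above 160 mg/dL, "must be treated aggressively with oral hypoglycemic agents and/or insulin as clinically indicated while continuing on MLN0128 treatment". It sets no upper grade and makes no exception.

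Protocol Section 6.3.1, the phase 2 dose-modification rule, adds: "MLN0128 administration should be withheld for MLN0128-related toxicities that are" Grade 3 or higher "despite supportive treatment per standard clinical practice". It also requires that the sponsor's "project clinician should be contacted before any dose modification in MLN0128 for any patient in the study".

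**The concern.** The text and the table give opposite instructions on the same question, whether the patient takes the next dose, for every patient above 250 mg/dL. The protocol does not say which one controls. The text uses mandatory language, while the table is introduced as guidance, so a site cannot settle the matter from the wording alone.

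What is at stake is patient safety and consistent conduct across roughly 40 centers. A literal reader of the text goes on giving the investigational drug to a patient whom the table would hold. The table's resume, reduce and stop steps all start from a hold, so a site that never holds may never apply them. Sites that read the section differently would also feed different data into the SAP summaries of doses held (Section 7.7.3), relative dose intensity (Section 7.7.2) and adverse events leading to dose modification (Section 7.11.1).

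**Working it through.** No sample size, error rate or event count is involved, so the check is a comparison of the provisions.

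**Step 1: text against table, by glucose range (both in Protocol Section 6.7.1).**

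| Fasting glucose | Grade | Text | Table 6-1 | Agree? |
|---|---|---|---|---|
| >160 to 250 mg/dL | 2 | treat, MLN0128 continues | no dose change | yes |
| >250 mg/dL | 3 or higher | treat, MLN0128 continues | hold until Grade 2 or lower | no |

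The conflict covers the whole Grade 3 or higher range and nothing below it. The qualifier about clinical indication in the text attaches to the choice of glucose-lowering therapy. It does not make an exception to continuing MLN0128.

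**Step 2: which of the two is the outlier?** Instruction for MLN0128 at Grade 3 or higher in each event table of Section 6.7:

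- Table 6-1, hyperglycemia: hold.
- Table 6-2, hyperlipidemia: hold at Grade 3, discontinue at Grade 4.
- Table 6-3, oral mucositis: hold at Grade 3, discontinue at Grade 4.
- Table 6-4, rash: hold.
- Table 6-5, nausea and vomiting: hold.
- Table 6-6, pneumonitis: interrupt at Grade 3, discontinue at Grade 4.

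Six of six hold, interrupt or stop, and none continues. The sentence in the text stands alone.

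**Step 3: does another rule force a hold at the first reading above 250 mg/dL?**

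- Section 6.3.1 applies to phase 2, to toxicity related to MLN0128, and only when it is Grade 3 or higher in spite of supportive treatment. A first reading, before glucose-lowering therapy has been tried, need not meet that condition.
- In phase 1b, Section 6.2 interrupts dosing for dose-limiting toxicities, but its general nonhematologic criterion exempts Grade 3 hyperglycemia lasting 14 days or less.
- The duty to contact the project clinician arises before a dose modification. A site that simply keeps dosing makes no modification, so the duty is not triggered.

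Table 6-1 is therefore the only provision that plainly requires an immediate hold, and it is the one that the text contradicts.

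**The case against.** The best case for leaving the text alone is that the sentence is not a dosing rule. Its main instruction is to treat the glucose, and the paragraph is presented as help with starting glucose-lowering drugs. Dosing has its own labeled column in Table 6-1, where an investigator would look, and the Grade 3 or higher row there is explicit. Continuing treatment could also mean only that the patient is not permanently taken off the drug, since the SAP counts a temporary hold separately from permanent discontinuation. Finally, the practical reach looks small. Section 6.7.1 reports that earlier episodes were mainly Grade 1 or 2 and that hyperglycemia stopped being dose-limiting once early treatment became standard. Daily home testing, with notification at 150 mg/dL or above, also brings high readings to study staff.

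Much of this stands. The table is the likely intent, the situation is probably infrequent, and a persistent related Grade 3 episode in phase 2 would be withheld under Section 6.3.1 as well. Three things do not follow. Reading the clause as meaning only that the drug is not permanently stopped is possible but is not its plain sense. The notification steps bring the reading to staff but do not tell them which instruction to obey. And a likely intent is not a stated order of precedence.

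**Conclusion.** The contradiction is real and sits in current, operative text. Its scope is fasting glucose above 250 mg/dL (Grade 3 or higher), where the text continues MLN0128 and the table holds it. From above 160 to 250 mg/dL there is no conflict. The sentence is too broad, and the table, supported by the other five event tables, is very probably the intended rule.

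The documents give no Grade 3 hyperglycemia rate, so the number of patients affected cannot be estimated. No effect on CBR-16, on the futility boundaries or on error rates is claimed. The conclusion rests on the ordinary meaning of the clause about continuing treatment and on the absence of any precedence statement. It should be fixed on patient-safety grounds, because whether to dose above 250 mg/dL needs a single answer.

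**What to change.** In Protocol Section 6.7.1, limit the clause about continuing MLN0128 to Grade 2 (above 160 to 250 mg/dL), and add a sentence such as: *At Grade 3 or higher (above 250 mg/dL), hold MLN0128 and resume, reduce or stop it per Table 6-1, which governs hyperglycemia.* Notify the sites of the correction.

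The cost is one edited sentence, one added sentence and a site communication. Table 6-1 does not change, and no procedures or data are added.

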**6.7.2 Management of Hyperlipidemia**

Guidance on MLN0128 dose modification for patients with hyperlipidemia is provided in [Table 6-2](#).

**Table 6-2 Management of Hyperlipidemia**

Grade	Description	Treatment	MLN0128 Dose Modification
1	Cholesterol: >ULN - 300 mg/dL Triglycerides: > 150-300 mg/dL	None	None
2	Cholesterol: >300-400 mg/dL Triglycerides: >300-500 mg/dL	Treat hyperlipidemia according to standard guidelines. Triglycerides $\geq$ 500 mg/dL should be treated urgently due to risk of pancreatitis.	Maintain dose if tolerable. If toxicity becomes intolerable, interrupt MLN0128 dosing until recovery to $\leq$ Grade 1. Reinitiate at same dose.
3	Cholesterol: >400-500 mg/dL Triglycerides: > 500-1000 mg/dL	Same as for Grade 2	Hold dose until recovery to $\leq$ Grade 1, then restart with a dose reduction (a).
4	Cholesterol: >500 mg/dL Triglycerides: >1000 mg/dL	Same as for Grade 2	Discontinue treatment.

**Prevention/Prophylaxis**

- Recommend lifestyle modifications, as appropriate (balanced diet, limited consumption of alcoholic beverages, increased physical activity).

QD $\times$ 5D=once daily for 5 days each week.

(a) Phase 1b Part 1 cohorts: for patients receiving a starting dose of 5 mg, reduce by 20% (to 4 mg). If dose modification is required for patients receiving  $\leq$ 4 mg QD, then the frequency of dosing should be decreased to QD $\times$ 5D, rather than decreasing the daily dose administered. For all other patients: the initial dose reduction should be from 4 mg to 3 mg, with further reduction to 2 mg if necessary.

### 6.7.3 Management of Oral Mucositis

Guidance for the management of oral mucositis is provided in [Table 6-3](#).

**Table 6-3 Management of Oral Mucositis**

Grade	Description	Treatment	MLN0128 Dose Modification
1	Asymptomatic or mild symptoms	Nonalcoholic mouth wash or 0.9% salt water rinse; consider topical corticosteroids at earliest signs of mucositis.	None
2	Moderate pain not interfering with oral intake; modified diet indicated	Topical analgesic mouth treatments; topical corticosteroids; initiate antiviral or antifungal therapy, if indicated.	Maintain dose if tolerable. If toxicity becomes intolerable, interrupt MLN0128 dosing until recovery to ≤Grade 1. Reinitiate at same dose.
3	Severe pain interfering with oral intake	Same as for Grade 2; consider intralesional corticosteroids.	Hold dose until recovery to ≤Grade 1, then restart with a dose reduction. (a)
4	Life-threatening consequences	Same as for Grade 2; consider intralesional corticosteroids.	Discontinue treatment.

**Prevention/Prophylaxis**

- Consider initiation of a nonalcoholic mouth wash or 0.9% salt water rinses 4-6 times daily with start of therapy before signs of mucositis develop.
- Avoid using agents containing hydrogen peroxide, iodine, and thyme derivatives in management of stomatitis as they may worsen mouth ulcers.

QD×5D=once daily for 5 days each week.

(a) Phase 1b Part 1 cohorts: for patients receiving a starting dose of 5 mg, reduce by 20% (to 4 mg). If dose modification is required for patients receiving ≤4 mg QD, then the frequency of dosing should be decreased to QD×5D, rather than decreasing the daily dose administered. For all other patients: the initial dose reduction should be from 4 mg to 3 mg, with further reduction to 2 mg if necessary.

### 6.7.4 Management of Rash

Guidance for management of rash is provided in [Table 6-4](#).

**Table 6-4 Management of Rash**

Grade	Description	Treatment	MLN0128 Dose Modification
≤2	Macules/papules covering ≤30% body surface area with or without symptoms	Consider treatment with topical steroid cream/ointment and/or oral antihistamines.	None
≥3	Macules/papules covering >30% body surface area with or without symptoms	Consider treatment with topical steroid cream/ointment, oral antihistamines, and/or pulsed steroids.	Hold until ≤Grade 2; resume MLN0128 based on timing of recovery: ≤2 weeks: reduce dose. (a) >2 weeks: stop MLN0128 and discontinue patient from the study.

QD×5D=once daily for 5 days each week.

(a) Phase 1b Part 1 cohorts: for patients receiving a starting dose of 5 mg, reduce by 20% (to 4 mg). If dose modification is required for patients receiving ≤4 mg QD, then the frequency of dosing should be decreased to QD×5D, rather than decreasing the daily dose administered. For all other patients: the initial dose reduction should be from 4 mg to 3 mg, with further reduction to 2 mg if necessary.

### 6.7.5 Management of Nausea and/or Vomiting

Guidance for the management of nausea and/or vomiting is provided in [Table 6-5](#).

**Table 6-5 Management of Nausea and/or Vomiting**

Grade	Description	Treatment	MLN0128 Dose Modification
≤2	Loss of appetite with or without decreased oral intake; 1-5 episodes of vomiting within 24 hours	Maximize antiemetic therapy; consider IV fluid hydration.	None
≥3	Inadequate oral intake; ≥6 episodes of vomiting within 24 hours	Maximize antiemetic therapy; initiate tube feeding, IVF, or TPN.	Hold until ≤Grade 1; resume MLN0128 without dose modification.

#### Prevention/Prophylaxis

Prophylactic use of antiemetic, antinausea, and antidiarrheal medications is encouraged, and these may be administered before each dose of MLN0128 as needed throughout the study.

IVF=intravenous fluids, TPN=total parenteral nutrition.

